#### Access to patient records

At referral to the research facility, the healthcare professional involved will forward relevant information to the researchers involved in the trial. Only data concerning patients and parents who have shown interest in the study will be disclosed to the study. The information includes identification data, contact data and demographic data, such as gender and age, as well as racial background and health information relevant to the study, e.g. visual acuity, refraction, biometrics, retinal examinations and other ophthalmological and systemic diseases (e.g. cardiovascular disease, respiratory disease, rheumatologic disease, musculoskeletal disease, developmental disorders and delays).

At the time the patient and parents consent to study participation, they accept that the Danish Medicines Agency, sponsor (i.e. [name], sponsor-investigator), investigators (i.e. researchers at the Department of Ophthalmology at Rigshospitalet; the Department of Ophthalmology at Aarhus University Hospital, and the Department of Ophthalmology at Vejle Hospital) and monitor (i.e. GCP units at Copenhagen University Hospital, Aalborg and Aarhus University Hospitals, and Odense University Hospital) may have direct access to obtaining relevant health information in the patient record including electronic records for quality control and monitoring.

#### Efforts to maximize adherence to treatment

If the patient and parents consent to study participation they will be offered to use artificial tear eye drops until the baseline visit to assess their ability to give the child eye drops each day throughout the 2-year treatment phase. The run-in phase will have an expected duration of approximately 1-4 weeks. The artificial tear eye drops will be distributed free of charge from the research facilities and is not regarded as trial medication. The summary of product characteristics of the artificial tear eye drops is available in the investigators brochure.

To assess the patient and parents' compliance level, the parents will receive written instructions at each planned visit for overview and checkmark of daily use of trial medication. The schedule will show which bottle (bottle number) the parents should use for each specific date interval. The written instruction works as a diary for trial medication use. For each week day in the date interval the parents can check mark that the eye drops have been (or not been) used as planned and make a optional comment. The written instruction filled out with check marks and notes comments by the parents as needed will be handed back to the researcher at each subsequent study-visit.

An example of the written instruction (*Dryppeskema til forsøgslægemidlet* in Danish) is attached as separate appendix.

At each visit during use of trial medication, the parents will additionally be asked how many days they have administered the trial medication as prescribed on an average week since last visit.

Patients and parents with a 75% compliance rate will be considered compliant.

#### Trial medicinations, procedures for receival and internal check-up

All trial medication (including placebo eye drops) will be manufactured and delivered from Skanderborg Apothecary (a simplified IMPD is provided in the investigators brochure). Upon receival of trial medication (including placebo), medication will be registered, handled and stored according to local guidelines. Trial medication will be kept in a locked room with logging of temperature. Any person associated with the study and to whom the task of receiving and registering trial medications has been delegated will be able to receive and perform internal check-up of trial medication. Information regarding this will be kept in trial master file.

## Sample size and data analysis

The primary endpoint of the present study is the mean change in axial length 36 months after baseline. Axial length is strongly related to the refraction of the eye and since we do not have valid data for axial length elongation in Danish myopic children, the power calculations have been performed using the refraction (in spherical equivalent) as a surrogate measure. A progression in untreated childhood myopia of  $-1.2 \pm 0.69$  diopters yearly has been shown in Asian children (ATOM1 study). (33) A similar myopia progression rate has been documented in untreated Danish school children. (42) Given a significance level (alpha) of 0.05 and a statistical power (type 2 error) of 80%, a study size of 21 patients in each interventional arm will be needed, assuming a difference in myopia progression of 50% after 36 months. In order to compensate for the study length and drop-out rates and unknown effect of low-dose atropine in non-Asian children, 50 patients will be included in each interventional arm.

#### Examinations

All examinations are non-contact methods that are used in daily clinical routine on children. A schematic presentation of the examinations during the study is shown in Figure 2 (see below). Expected duration of the different examinations is indicated in parentheses in the following.

Examination at screening visit (approx. 1 hour 30 min to 2 hours):

- Best corrected (using "push plus" refraction principle) visual acuity using the HOTV chart that is based on the same principle as the Early Treatment Diabetic Retinopathy study (ETDRS) chart.
- Cycloplegic auto-refraction performed at least 30 minutes after the last of two drops of Minims® (Bausch & Lomb, Chauvin Pharmaceuticals Ltd., UK) cyclopentolate 1% separated 5 minutes apart. A minimum of 5 readings are made. In situations of unstable fixation, readings are eliminated if cylinder values deviate more than 1 diopter from values obtained during stable fixation and/or obvious incorrect readings.

- Intraocular pressure (Icare® TA01i, tonometer, Icare Finland Oy, Vantaa, Finland) with a minimum of 5 readings.
- Axial length measurements (IOLMaster® 700, Carl Zeiss Meditec AG, Jena, Germany). Separate measurements are recorded until 5 readings variating less ≤ 0.05 mm are obtained.
- Anterior Eye Segment Tomography by Scheimpflug imaging (Pentacam®, OCULUS Optikgeräte GmbH, Wetzlar, Germany).
- Pupil diameter measurements under different light intensities.

**NB!** If the screening visit and baseline visit take place less than 1 month in between, examinations performed at the screening visit will not be repeated at the baseline visit.

#### Standard examinations at baseline and month 3, 6, 12, 18, 24, 30 and 36 (approx. 2 hours):

- Best corrected (using "push plus" refraction principle) visual acuity using the HOTV chart that is based on the same principle as the ETDRS chart.
- Cycloplegic auto-refraction performed 30 minutes after the last of two drops of Minims® (Bausch & Lomb, Chauvin Pharmaceuticals Ltd., UK) cyclopentolate 1% separated 5 minutes apart. A minimum of 5 readings are made. In situations of unstable fixation, readings are eliminated if cylinder values deviate more than 1 diopter from values obtained during stable fixation and/or obvious incorrect readings. In situations of more than 5 valid readings, the number is reduced by eliminating readings from the beginning alternating with the end of the set of measurements until 5 readings remain.
- Intraocular pressure (Icare® TAO1i, tonometer, Icare Finland Oy, Vantaa, Finland) with a minimum of 5 readings.
- Axial length measurements (IOLMaster® 700, Carl Zeiss AG, Oberkochen, Germany). Separate measurements are recorded until 5 readings variating less ≤ 0.05 mm are obtained.
- Anterior Eye Segment Tomography by Scheimpflug imaging (Pentacam®, OCULUS Optikgeräte GmbH, Wetzlar, Germany).
- Pupil diameter measurements under different light intensities.
- Swept Source Optical Coherence Tomography chorio-retinal images (DRI OCT Triton, Topcon, Hasunuma-cho, Itabashi-ku, Tokyo, Japan) at baseline and month 6,12,18,24,30 and 36.
- Near visual acuity assessed using best-corrected distance spectacle correction with a reduced logarithm of the minimum angle of resolution (logMAR) reading chart placed at 40 cm under welllit conditions.

 Near point of accommodation measured using a Royal Air Force near point rule using bestcorrected distance spectacle correction. Accommodation amplitude is calculated as the inverse of near point of accommodation.

Figure 2: Time schedule of the study.

#### Monofocal spectacle and soft contact lenses

Several recent studies and reports conclude that undercorrection of myopia is associated with higher rate of myopic progression in children. (28,43-46) Hence, the patients will be provided full correction of their refractive error during the entire trial period. The parents will receive a maximum annual compensation of 1000 DKK at baseline visit, 12 months visit and 24 months visit designated the acquisition of full refractive correction. The patient and parents decide if spectacles, contact lenses or both are preferred as refractive correction but only monofocal refraction may be purchased. At baseline visit, 12 months visit and 24 months visit, the patient and parents will receive a refractive prescription to show the optician when acquiring new refractive correction. The parents will be instructed to submit documentation for each purchase by email within one month. For each new acquisition of refractive correction, only the purchased amount up to a maximum of 1000 DKK will be compensated. The compensation will be transferred to desired bank account appointed by the parents when submitting the documentation of purchase.

If a patient experiences glare or their parents are worried of excessive light exposure as a result of trial medication, the patient will be offered photochromatic spectacles (that darken on exposure to ultraviolet light). If a patient experiences difficulty with near vision as a result of trial medication, the patient will be offered reading add as bifocal spectacles. In both cases, the investigator will decide upon clinical

assessment if photochromatic or bifocal spectacles are indicated. If deemed relevant, the parents will be instructed in the acquisition and compensated the full amount of purchase. The purchase of photochromatic or bifocal spectacles will not be compensated if the investigator finds it irrelevant or if the investigator is not consulted before the purchase.

## Endpoints

#### Primary endpoints

- Axial length elongation at 36 months
- Change in spherical equivalent at 36 months

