## Hypothesis

The main hypotheses tested in this study are:

- 0.01% atropine one drop nightly reduces the progression of childhood myopia in Danish children.
- 0.01% atropine one drop nightly is safe and with no significant side effects.
- A 6-month loading dose of 0.1% atropine followed by a 0.01% atropine maintenance dose is superior to single 0.01% atropine.
- 0.1% atropine one drop nightly is safe and has tolerable side effects.

- The rebound effect after stopping both atropine regimens is limited.
- Choroidal thickness is a predictor for the progression of childhood myopia.

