## Methods

#### Study design

The study is designed as a randomized, double-masked, multicenter, 36-month prospective, phase II 1:1:1 study of safety and efficacy of 0.1% atropine loading dose to single 0.01% atropine versus placebo. In phase 1 (treatment phase), the participants will be randomized in a 1:1:1 ratio to receive 0.1% atropine loading dose for 6 months followed by 0.01 % atropine for 18 months (n=50) versus 0.01% atropine (n=50) or placebo (n=50) for 24 months. The atropine is administered as one eye drop daily in each eye at bedtime. In phase 2 (washout phase), treatment will be stopped and the participants monitored for 12 months. A schematic presentation of the 3 interventional groups are shown in Figure 1.

Figure 1: A schematic presentation of the 3 interventional groups.

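### The plan names one primary endpoint in its sample-size section but two in its endpoint list, with no either/both rule, and it gives no rule for testing the three arms

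*Combined protocol and SAP*

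**What the plan says.** Sample size and data analysis is explicit: "The primary endpoint of the present study is the mean change in axial length 36 months after baseline". It explains that valid axial length data in Danish myopic children were lacking, so "the power calculations have been performed using the refraction (in spherical equivalent) as a surrogate measure". In that section spherical equivalent is a planning device and not an outcome on which success is judged.

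The list under Primary endpoints has two entries: axial length elongation at 36 months and "Change in spherical equivalent at 36 months". Neither is ranked above the other, and nothing says whether one or both must be positive.

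On the arms, Study design describes a 1:1:1 randomised phase II trial with three groups, a "study of safety and efficacy of 0.1% atropine loading dose to single 0.01% atropine versus placebo". Hypothesis opens with "The main hypotheses tested in this study are" and includes two efficacy statements: "0.01% atropine one drop nightly reduces the progression of childhood myopia in Danish children" (comparator not named; placebo follows from the design) and "A 6-month loading dose of 0.1% atropine followed by a 0.01% atropine maintenance dose is superior to single 0.01% atropine". Loading dose against placebo is not on that list and is only implied by Study design.

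The only significance level in the document is the 0.05 in the sample-size section. No section names a statistical test, a primary contrast, a testing order, a global test or an adjustment.

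**The concern.** A reader of the final report needs to know which result decides whether the trial succeeded. Here that is open in two ways. First, two current sections of the same document disagree on whether spherical equivalent is primary. If axial length and refraction give different answers, each has a section of the plan to support it as the deciding result. Second, with three arms and no ranking, any of two or three contrasts could be put forward as the main finding.

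The first problem is a contradiction in the text. The second is an omission. They interact, because a rule for the arms does not settle which endpoint it applies to, and settling the endpoint does not say which contrast counts.

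**Working it through.** **1. What the stated alpha covers.** Inputs from Sample size and data analysis: yearly progression 1.2 D, SD 0.69 D, 50% reduction (0.6 D), alpha 0.05, power 80%.

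- d = 0.6/0.69 = 0.870
- n = 2(1.960 + 0.842)²/0.870² = 20.8, so 21 per arm, as stated. (The t-test version gives 21.8, so 22.)
- A one-sided test would give 17, so the stated figure implies a two-sided test, although the plan does not say so.

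The 0.05 therefore belongs to one two-arm, two-sided comparison on one endpoint. Nothing in it allows for a second endpoint or contrast.

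**2. False-positive risk on axial length alone, if each contrast were tested at two-sided 0.05.** Assumptions: all arms truly equal, near-equal arm sizes, one final analysis.

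- Two contrasts that share an arm have test statistics correlated at 0.5 in absolute value. Risk = 1 − P(|Z1| ≤ 1.96 and |Z2| ≤ 1.96) = 9.1%. This applies both to the two active arms against placebo and to the pair listed under Hypothesis.
- All three pairwise contrasts: the studentized range for three groups, exceeding 1.96 × √2 = 2.77, gives 12.2%.
- Simulation with t-tests at 32 per arm agrees (about 9% and 12%). The figure of 32 is 97/3 from the number randomised in Study period; the actual split is not given.
- Counting only false claims in the hypothesised direction: about 4.5-5% for two contrasts and 6.5-7% for three, against 2.5% for a single test.

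**3. If either endpoint may count.** This needs the correlation between the endpoints, which the documents do not give. For an assumed range of 0.5 to 0.95, the unadjusted two-sided risk falls from about 16% to 12% for two contrasts, and from about 21% to 15.5% for three.

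**4. Do simple rules control it?** On axial length alone, a global three-group test at 0.05 that gates the pairwise tests gives 4.9-5.1% under the global null, and a fixed sequence gives the same. With exactly three arms the gate also holds when only one null hypothesis is true (5.0-5.1% in simulation).

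**5. What the rules cost in power.** For a single comparison the noncentrality is d√(n/2). At 32 per arm this is 0.870 × 4 = 3.48 on 62 degrees of freedom, giving 93%. At 24 per arm (an assumed 25% dropout, 0.75 × 32) it is 3.01 on 46, giving 84%. At half the effect and 32 per arm it is 1.74, giving 40%. The other figures are simulated with both active arms equally effective:

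| Scenario | Each placebo comparison, unadjusted | With gate | Second claim in a fixed sequence |
|---|---|---|---|
| 32 per arm, d = 0.87 | 93% | 91% | 88% |
| 24 per arm, d = 0.87 | 84% | 80% | 74% |
| 32 per arm, d = 0.435 | 40% | 32% | 24% |

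The opening test in a fixed sequence keeps the unadjusted power.

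If instead 0.01% has half the effect and loading the full effect (32 per arm), the gate lowers loading against placebo from 93% to 87%. A fixed sequence that starts with 0.01% against placebo reaches that claim only about 40% of the time.

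All these power figures borrow the yearly refraction effect. They are not estimates for axial length at 36 months, which follows 12 months off treatment.

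**The case against.** The strongest reply has three parts.

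- **Silence is not a plan to test unadjusted.** This stands. A reader might infer that the trial carries a 9% or 12% error rate. The documents do not support that, because they describe no unadjusted testing. The rates are conditional, and the 12% also needs a contrast that the Hypothesis section does not list.
- **The hypotheses are directional and the trial is phase II.** Both listed efficacy statements predict benefit, so half or more of the two-sided 9% is error in a direction that nobody would claim as success; the 4.5-5% figure is the fairer one for benefit claims. Whether separate hypotheses in a phase II trial need familywise control is debated. This also stands, and it makes the arm rule the weaker half of the point. It does not remove the need to say which contrast is primary, since the plan presents these as its main tested hypotheses.
- **The two endpoints are closely related, so listing both does little harm.** This does not resolve the matter. The plan calls axial length strongly related to refraction but gives no correlation, and even at 0.95 allowing either endpoint moves the three-contrast figure from about 12% to about 15.5%. Nor does a high correlation say which result governs when they differ.

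Masked analysis, promised under Blinding, does not choose an endpoint or a contrast either. Results by coded group could still inform that choice.

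**Conclusion.** The endpoint contradiction is firm and rests on the text alone: one primary endpoint in the sample-size section, two in the endpoint list, and no success rule to connect them. The documents do not settle which section governs.

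The missing rule for the arms is a real omission of lesser weight. Its size is conditional on unadjusted testing, all arms equal and no allowance for interim looks: about 9% for the two listed contrasts and about 12% with the implied third, two-sided, on axial length alone. Letting either endpoint count would raise this by an amount that depends on the unknown endpoint correlation.

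This should be fixed, but it does not show that the trial's results will be invalid. A single endpoint and a simple rule, settled in time, bring the overall risk to about 5%.

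**What to change.** 1. **Reconcile the two sections.** The simplest way is to keep axial length at 36 months as the only primary endpoint and make spherical equivalent the first key secondary, which matches the explicit sentence in the sample-size section. If both are meant to be primary, say whether either or both must succeed, and make the testing rule cover both.
2. **In the same amendment, settle the arms.** State in Sample size and data analysis which contrast is primary, or adopt one rule at overall two-sided 0.05: a global three-group test that gates the pairwise tests, or a fixed sequence in an order that the sponsor chooses. Report every contrast with a 95% confidence interval in any case.
3. **Label the sample size.** State that 21 per arm and 80% power refer to one active-versus-placebo comparison on yearly refraction.
4. **Fix this before any efficacy comparison by arm is seen**, coded or unmasked, including at the interim analyses set out under Criteria for aborting the study. If one has been seen, disclose it; the rule would then no longer count as prespecified.

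**Cost.** A protocol amendment, with no new patients or measurements. With both active arms equally effective, the gate costs each placebo comparison about 2 points of power in the most favourable case shown, about 4 at 24 per arm, and about 8 at half the effect. For the second claim of a fixed sequence the losses are about 5, 10 and 16 points. If the active arms differ, the order of a fixed sequence matters more than these averages suggest, so the sponsor should choose it deliberately.

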#### Secondary endpoints

- Adverse effects and reactions
- Change in choroidal thickness
- Change in ocular biometry (i.e. keratometry, anterior chamber depth, lens thickness, vitreous axial distance)
- Change in higher-order aberrations

## Risks, side effects and inconveniences

The use of atropine 1% eye drops has been approved for cycloplegia, mydriasis and penalization of the healthy eye in the treatment of amblyopia. The most frequently reported side effects of atropine 1% eye drops include photophobia, blurred vision, decreased lacrimation and allergic reactions such as papillary conjunctivitis, contact dermatitis and lid edema. Systemic side effects rarely occur but include anticholinergic effects such as dryness of skin, mouth and throat from decreased secretion from mucus membranes, flushing, gastrointestinal symptoms, urinary retention and tachycardia. Systemic absorption may be reduced by gently compressing the lacrimal sac at the medial canthus for a minute during and following the instillation of the drops. This blocks the passage of the drops via the naso-lacrimal duct to the wide absorptive area of the nasal and pharyngeal mucosa.

The use of low-dose atropine has not yet been approved for the treatment of myopia and is not yet commercially available. In the ATOM 2 study, the reported side effects of atropine 0.01% and 0.1% were low. The pupil size under both photopic and mesopic conditions increased only 1 and 3 millimeters,

respectively, in the 0.01% and 0.1% group. (32) Accommodation amplitude in the 0.01% group was reduced to only 11.3 diopters (from 16.2 diopters) compared with a reduction to 3.8 diopters (from 16.7 diopters) in the 0.1% group. The mean reduction in accommodation amplitude over 2 years treatment was 4.6 diopters and 10.1 diopters in the atropine 0.01% and 0.1% group, respectively. (32) In functional terms, the changes in accommodation meant that near visual acuity was not significantly impaired in the 0.01% group, whereas deficiencies were noted in the 0.1% group. (32) Mean distant best-corrected visual acuity (BCVA) was not affected by low-dose atropine, although 13% in both groups reported mild distance blur. (32) Regarding adverse reactions attributable to atropine, allergic reactions were most frequent in the ATOM 2 study with 3.2% experiencing allergic conjunctivitis and 0.8% experiencing an allergy-associated dermatitis, all of which were in the 0.1% group. From a total of 400 children, 6 children had other eye symptoms, 5 of which could be attributed to atropine treatment, including 1 case of ocular irritation and 1 case of blur in the atropine 0.01% group, and 2 cases of ocular irritation and 1 case of intolerable glare in the atropine 0.5% group. All reported side effects were reversible on stopping medication. No adverse events were deemed to be related to the use of atropine at any concentration. (32)

Patients who experience adverse effects during the study will provide data for the study to determine the rate of complications. Since the sample size calculation was made to account for dropout, additional inclusion of participants to replace excluded participants is not intended.

